# 3.5 The HeraBEATTM Application (App)

The HeraBEATTM App. (Figure 2) runs on a Smartphone (Android version 6 and above and iOS version 11 and above). The application communicates with the HeraBEATTM device over Bluetooth low energy (BLE), controls the operation of the device, and receives the FHR and MHR value in real time for displaying numerally and graphically to the user. The application can also record these values for later review and transmission to a healthcare provider.

Figure 2. Representative HeraBEATTM app screens

# **3.6 Device Classification**

Fetal monitoring devices, including fetal Dopplers, which acquire and display the fetal heart rate and/or uterine contractions, are FDA Class II medical devices.

	system speemeation	
Safety	Complies with	IEC/EN 60601-1, 60601-1-2, 60601-1-11, 60601-2-37
Classification	Anti-electric Shock Type	Class II electrical device when AC/DC adapter connected. Otherwise Internally powered equipment.
	Anti-electric Shock Degree	Type BF equipment
	Degree of Protection against Harmful Ingress of Water	IP22 Protection against falling drops of water when unit is tilted 15°.
Physical Characteristics	Device size	88 x 37 mm, 3.5 x 1.5 inch (Diameter × Height, ±0.08inch
	Device weight	Approximately 4.58 Ounce
Operating	Temperature	From 41°F up to 104°F
Environment	Humidity	From 5% up to 90% RH (non- condensing)
Storage/Transp ort Environment	Temperature	From -4°F up to 140°F
	Humidity	From 5% up to 95% (non-condensing)
	Light intensity	No direct sun light
	Pregnancy Week	12 to 42

# Table 1: 'HeraBEATTM', system specification

FHR Performance	FHR Measuring Range; Accuracy; Resolution	50 to 240 BPM; ±2BPM; 1 BPM		
	MHR Measuring Range; Accuracy; Resolution	45 to 240 BPM; ±2% or 1 BPM, whichever is greater; 1 BPM		
Auto Acquisition	stop	5 minutes of successful measurement		
Recommended Ultrasound Transmission Gel		Aquasonic 100 Ultrasound Transmission Gel, by Parker Laboratories.		
Power consumption	on	< 2 W		
Rechargeable	Nominal Capacity	3.7VDC, 1250 mAh		
Li-ion Battery	Continuous Work Time	4 hours (with a new battery)		
	Power Input	5 V DC, >0.3A		
	Charge Time	4 hours		
Ultrasound (NEMA/FDA)	Nominal Frequency	2 MHz ±10%		
	Ultrasonic Output Power (P)	70mW		
	Peak rarefactional pressure ( p r )	0.03 MPa		
	Ultrasonic Output Intensity (I sata )	$\leq 20 \text{mW/cm}^2$		
	Mechanical Index (MI)	0.02		
	Thermal index (TIS; TIB)	0.26; 0.7		
	Measurement Mode	Continuous Wave Ultrasound Doppler		
	Effective Radiating Area of Transducer	$4.9\pm0.5 \text{ cm}^2$		
BLE specification	frequency band of transmission	
 
2.4 – 2.5 GHz
 
Channels (2MHZ spacing)
 
3 Advertising channels @ 2402, 2426
 
2480Mh
 
36 data channels
 
		
	frequency characteristics of the modulation	DSSS: GFSK (modulation index = 0.5)		
	Maximum RF Input	-10 dBm		
	Typical Receive Sensitivity	-94 dBm		

Maximum RF Tx Output	+4 dBm
Power	

# **3.7 The HeraBEATTM Functional Description**

The operation of the device starts when the application is open and the HeraBEATTM device is turned-on:

- Step 1: Achieving Bluetooth (BLE) connectivity between the HeraBEATTM device and the HeraBEAT App. Pairing is obtained following a onetime PIN code entered by the user. The user is then directed to register and enter her last menstrual cycle (LMP). An estimated fetal gestational age is calculated. Once the application is open, the application automatically searches for and connects to the HeraBEATTM device.
- 2. Step 2: The user must apply the provided gel to the bottom of the HeraBEAT™ device.
- 3. **Step 3:** The User presses the "START" command in the HeraBEATTM App., and is guided to start searching for FHR signals by a built in Guided Search.
- 4. At this time, the device sends the App. the quality index of the FHR (QFHR), the QFHR index indicate to the application when the location and position of the device over the abdomen is satisfactory and FHR signal is measured.
- 5. When the QFHR is appropriate, the application instructs the user to hold the position over the abdomen and the device sends the FHR and MHR values for display and recording within the mobile App.
- 6. **Step 4:** The FHR and MHR measurements stop when either the user presses the "STOP" command or closes the application, or a predetermined time period has been reached.

Complete instructions for use of the HeraBEATTM are provided in *Appendix A*.

HeraBEATTM dashboard layout and specification provided in *Appendix B*.

The following is a list of HeraBEAT™ safety claims:

- HeraBEATTM works at low voltage (5V) which is supplied from an internal rechargeable battery (tested per IEC 60601-1).
- HeraBEATTM device material is isolated and made of electric non-conducting material. In addition, the device does not operate while charging.
- HeraBEATTM transmits ultrasonic energy, at a maximum intensity of 20mW/cm2, according to IEC 60601-2-37 'Medical electrical equipment Part 2-37: Particular requirements for the safety of ultrasonic medical diagnostic and monitoring equipment'
- The device turns off if not connected to the mobile application for several seconds.
- All materials are biocompatible and approved for use on skin surface.

• HeraBEATTM controls the temperature level inside the device to assure that the device temperature remains below the safe temperature limit. In addition, a built-in-test (BIT) is implemented to verify the correct functioning of temperature Sensor.

The device conforms to risk management best practices according to ISO 14971:2007 – Medical Devices – Application of Risk Management to Medical Devices.

#### 4.0 HeraBEAT™ Research Data to Date

A prospective feasibility clinical performance and usability validation study was performed using the 'Compass' (A previous brand name for the HeraBEATTM), Self-Administered Fetal Heart Rate Monitor in Pregnant Women in 2016, at Assaf Harofeh Medical Center and a private OBGYN clinic in Rishon Letzion, Israel. HeraMED Ltd. served as the study sponsor and [name]. served as the principal investigator. This study was conducted in compliance with the Israeli Ministry of Health regulations, the ethical principles of the Declaration of Helsinki, and the current Good Clinical Practices (GCP) set forth in EN ISO 14155 (2011) standard.

The study was a prospective, non-randomized, open-label, single center, single arm study, with end-to-end clinical and usability validation to evaluate the performance, usability and safety of the Compass system in pregnant women.

The objectives of this study were to validate the safety and performance of self-operation of the Compass by intended users in realistic use scenarios and conditions. The chosen scenarios represented all steps involved in performing FHR measurement, verifying user's understanding of labeling and instructions for use when using the device, verifying that potential users were able to perform self-selection prior to using the device and evaluate user's subjective perspective/satisfaction.

The study enrolled expectant mothers with confirmed 12 week gestation pregnancy. Twenty five (25) participants were screened and 23 were enrolled, completed and analyzed. Indication for use included expectant mothers  $\geq 18$  years, with singleton fetus, gestational ages of 12 weeks or greater and familiar with Smart phone usage. Exclusion criteria included multifetal gestation, maternal history of defibrillation, electro-surgery, and patients with external electrical stimulators, cardiac pacemakers or requiring use of MRI or other high frequency medical equipment.

Primary Endpoint for performance included an evaluation of the ability of participants to selfmeasure FHR with the device. Primary Endpoints for usability included an evaluation of the following: success rate of the user's ability to self-select the device in accordance with the label; success rate of the user in independently performing critical and essential tasks (objective measure) and user perspective of success (subjective measure, systematically collected) for critical and essential tasks. The Secondary Endpoint for safety included an evaluation by reporting the incidence and severity of all device related adverse events. The study consisted of a single visit, conducted on one day. Patients were self-selected during the screening process. Usability and performance of the device was evaluated by study personnel.

The feasibility study results were as follows:

- Performance success rate of Fetal Heart Rate detection was 100% (CI 85.2 100.00).
- The Pass/Fail success rate for all the usability critical and essential tasks was 100% in the following domains: 1. Self-Selection, 2. Task Performance: Training Material, Handling the Compass, Performing the Procedure, Performing the Switching Off.
- User Perspective of Success was evaluated by a post tasks questionnaire. Each question was evaluated on a scale from 1 to 5 (1. Strongly disagree; 2. Disagree; 3. Neither agree nor disagree; 4. Agree; 5. Strongly agree). Mean scores were calculated for each question. Results ranged from 4.3 to 5.0, indicating that expectant moms agreed or strongly agreed with the ease of use of the device.
- There were no safety issues or adverse events reported. Post-development testing indicated that the Compass System (now HeraBEATTM) was successful in achieving its per protocol efficacy and safety endpoints, usability and performance measures.

# 5.0 Study Methods

# 5.1 Overview

Primary Objective

- 1) To evaluate the functionality of HeraBEAT™ when self-administered by pregnant women by assessing the following:
  - a) Study participants' independent use of the device assessed by study personnel observation, including ability of participants to read and follow HeraBEATTM device instructions, and find fetal heart rate without assistance evaluated using the HeraBEATTM Independent Device Assessment Form. (*Appendix C*).
  - b) Data transmission from the device to the healthcare provider via a HIPAA compliant cloud-based server, assessed by evaluating the data transmitted to the healthcare provider from the HeraBEAT™ US device, including subject' success in finding FHR, time to find FHR, frequency of use, and clinical utility of the FHR/MHR data (*Appendix B*).

Secondary Objective

- 1) To evaluate the acceptability of HeraBEAT™ when self-administered by a pregnant women in the home by assessing the following:
  - a) Patient usability and ease of use assessment as measured by the System Usability Scale (SUS), *Appendix D*.
  - b) Impact on utilization of care as measured by urgent triage and/or emergency care visits for concerns regarding fetal well-being.

## 5.2 Research Design and Participants

We propose a single center randomized cross-over study in the outpatient obstetric setting at an academic institution in the mid-west, United States to test the functionality and acceptability of HeraBEATTM for self-administration by pregnant women.

# **5.3 Participant Selection**

This study will recruit low risk pregnant women, with singleton pregnancies, presenting for prenatal care at the Obstetrics and Gynecology Department at Mayo Clinic Rochester. No waivers or exemptions to any eligibility criteria will be permitted. Each criterion will be addressed and documented in the mother's case report form for eligibility assessment. Patients will be recruited as a convenience sample after eligibility is assessed.

# 5.4 Eligibility criteria

Inclusion Criteria:

- 1. At least 18 years of age
- 2. Able to speak, read and understand English
- 3. Able to provide informed consent (i.e. no impairments or barriers)
- 4. Owns a suitable iOS or Android device and demonstrates average control and basic understanding of using a smartphone (i.e. download App, operate BT etc.)
- 5. At least 12 weeks gestation, or following first OB provider visit with pregnancy confirmation
- 6. Pregnancy documented as low risk

Exclusion Criteria:

- 1. Any observed cranial or cardiac anomalies on formal ultrasound
- 2. Multifetal gestation
- 3. Maternal history of defibrillation
- 4. Maternal history of electro-surgery
- 5. Patients with external electrical stimulators, cardiac pacemakers or requiring use of MRI or other high frequency medical equipment
- 6. Clinical judgment that determines that the pregnancy is at high risk for complications that would require outpatient or inpatient monitoring for clinical care.

## 5.5 Study Design

As part of current standard of care, pregnant women are initially evaluated by an obstetric physician, nurse practitioner or midwife during the first trimester. During this visit, the study nurse will complete the assessment for eligibility criteria for low risk pregnant women. Upon confirmation of eligibility, the nurse will contact the study coordinator. The study coordinator will approach the patients with study information, ascertain interest in participation, and obtain signed informed consent from those interested.

Between 18 and 20 weeks gestation, all patients complete a fetal sonography assessment for fetal anatomy as part of routine prenatal care. An obstetric provider will review the results with the patient, and confirm that fetal anatomy is normal. Patients with abnormal fetal cardiac or cranial anomalies will be excluded from the study. If the patient interest remains, the study coordinator will confirm ongoing consent and randomize the patient into the study. This will be documented in the appropriate section of the patient's electronic medical records.

Study personnel (obstetric nurses or clinicians) will then provide patients with a study kit, containing the HeraBEATTM device or a standard fetal Doppler device (based on randomization assignment), discuss the limitations of both devices, and instruct patients on the range of normal fetal heart rate.

Study personnel will then observe the study subjects' independent self-administration of the devices in the prenatal clinic after patients receive a brief tutorial of the devices operation. Study subjects will be able to refer to the device instructions for use but will not receive assistance or prompts during this testing session. Study personnel will note any mistakes or difficulties by the subjects on the HeraBEATTM Independent Device Use Assessment Form (Appendix C). Once the observation period is completed, study personnel will document all observations, review and correct any errors made by patients during use of the device, assist patients in confirming accurate use, perform teach back, and provide the study subject with a device for home use. Patients will be instructed to call clinic or Triage with any questions or concerns regarding results of fetal monitoring at home. All calls and recommendations provided will be documented.

## 5.6 Schema

Patients will be instructed to monitor their fetus once weekly, using their assigned device, from 20 weeks to 36/37 weeks gestation. Patients using the HeraBEATTM device will have their FHR and MHR data displayed on their App, and uploaded to a HIPPA compliant cloud based server, which can be accessed by the healthcare provider for review (*Appendix B*). Patients using the standard handheld Doppler device will be given a study brochure for recording their weekly data. Patients using the HeraBEATTM device will be instructed to bring their device during their outpatient clinical appointments, for comparison of MHR and FHR during their routine clinic appointments using methods documented in *Appendix E*.

After approximately 8 weeks of monitoring, patients will complete a System Usability Survey (SUS Survey), *Appendix D* to assess ease of use of the device, then crossover to the alternate study product.

Patients who are randomized to HeraBEATTM from 20weeks gestation to 28 weeks gestation will be given the standard fetal Doppler. Patients who are randomized to the standard Fetal Doppler will switch to the HeraBEAT.TM At the conclusion of each patient device use (28 weeks and 36 weeks gestation), participants will complete the System Usability Survey (Appendix D) to assess ease of use of each device.

- 1- Nurse assesses eligibility criteria, ascertains mother's interest, and study coordinator will obtain consent and complete randomization Patients will be given home monitoring equipment after their fetal anatomy sonography is complete, inclusion/exclusion criteria confirmed and Patient Usability Form completed (Appendix C).
- 2- After 8 weeks of use, participants will complete the System Usability Scale (SUS) survey (Appendix D), return the first study device and crossover to the second device. An independent device use assessment (Appendix C) will be assessed by study nursing staff and completed for the second device.
- 3- At the conclusion of 8 weeks of self-monitoring with assigned device, participants will complete the System Usability Scale (SUS) survey to assess ease of use (Appendix D).

Prior to registering study participants, all eligibility criteria will have been met and fully documented. Mothers will be randomized by the study coordinator after completion of standard informed consent for participation in clinical research including permission to use Protected Health information.

Registration/randomization is available via the Study Data Management System (SDMS), a web application portal framework supported through Mayo Health Sciences Research.

## **5.7 Intervention**

All randomized participants will be assigned to an obstetric physician, midwife or combination of physician/nurse practitioner care team that will supervise care during her pregnancy. All laboratory tests, imaging, and standardized evaluations that ensure the safety of the participant and her fetus will be conducted in both arms of the study as per departmental protocol.

Participants will be instructed to seek care (per routine obstetric precautions) for any concerns regarding fetal wellbeing, irrespective of their FHR on home monitoring devices. No clinical decisions will be solely based on the results of home monitoring data. Data uploaded from the HeraBEATTM device will be monitored by trained study personnel via the HeraBEAT dashboard : https://hera-med.rmdy.health/CoachConsole/Account/Login. FHR abnormalities will be investigated, using standard obstetric clinical protocols.

All adverse events (AEs) experienced by the subjects while at home or in the clinic will be recorded on the HeraBEATTM study case report form and evaluated for type of event, severity, whether the AE qualifies as a serious adverse event (SAE), and relationship of the AE to the HeraBEATTM device use.

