## 5.9.3 Clinical/Practice Important Outcomes

Safety and Healthcare Utilization: Data will be captured from the medical record review and participant's report of any safety concerns. A medical record review will be conducted to capture

all in-office visits within the OB Clinic, all triage visits and any hospitalizations that were prompted by FHR monitoring obtained at home, and recorded on the study case report form.

Patient engagement with remote monitoring devices will be measured by the number of times patients record FHR or both MHR and FHR data. Participant compliance with instructions regarding frequency of device use will be assessed by reviewing the device use statistics gained from information automatically uploaded to the HIPAA compliant cloud storage each time the device is used (*Appendix B* and https://hera-med.rmdy.health/CoachConsole/Account/Login).

Participants who use the device more often than what is recommended will be re-instructed on appropriate use (once weekly).

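### Adverse events are rated for relationship to HeraBEAT only, although every woman also uses a study-issued standard Doppler for about half of home monitoring

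*Combined protocol and SAP*

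**What the plan says.** Section 5.2 sets the design: "We propose a single center randomized cross-over study in the outpatient obstetric setting". Section 5.5 has study staff hand out a kit with either HeraBEAT or a standard fetal Doppler, so both devices are issued by the study. Section 5.6 runs weekly home monitoring "from 20 weeks to 36/37 weeks gestation" and places the change of device after about 8 weeks, when women "return the first study device and crossover to the second device". The other sequence mirrors this: "Patients who are randomized to the standard Fetal Doppler will switch to the HeraBEAT".

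Section 5.7 governs adverse events. Capture is broad: "All adverse events (AEs) experienced by the subjects while at home or in the clinic will be recorded on the HeraBEAT" study case report form, with no restriction to the HeraBEAT period. Assessment is narrower. Each event is classified by type and severity, then by "whether the AE qualifies as a serious adverse event (SAE), and relationship of the AE to the HeraBEAT" device use. Relationship to the Doppler is not requested there or anywhere else.

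Other sections collect safety information without singling out a device:

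- Section 5.5 documents all calls about home monitoring results.
- Section 5.9.2 includes safety concerns in the usability survey, which Section 5.6 has completed after each device.
- Section 5.9.3 abstracts OB clinic visits, "all triage visits and any hospitalizations that were prompted by FHR monitoring obtained at home".

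Section 8.0 analyses women in the arm to which they were randomized and compares further outcomes between arms. It specifies no adverse-event table by device or by period.

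**The concern.** The causality question covers one of the two devices that the study puts in women's homes. During Doppler weeks the only relatedness question concerns a device that the woman has handed back or has not yet received. Followed as written, the plan can produce a count of device-related events for HeraBEAT and none for the Doppler.

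This bears on Hypothesis 2b in Section 1.0, which includes no adverse effect on maternal safety. Section 3.2 says that self-monitoring at home is not a standard approved use of Doppler devices, so the document does not treat home use of the comparator as already characterised. Ascertainment is already uneven: staff watch HeraBEAT uploads on a dashboard (Section 5.7), while Doppler readings go into a brochure (Section 5.6). Clinicians are unblinded (Section 8.0), and some study personnel hold equity in the manufacturer (Section 9.1). A symmetric causality question would make the safety report easier to defend.

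**Working it through.** The plan gives no figure for adverse events. Its only design figure is the 99.7% power for a 10-point SUS difference (Section 8.2), which cannot be reproduced because no SD, alpha or sidedness is stated. This point does not depend on it.

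**Step 1: how much device use lacks a matching causality question.** Inputs are 50 women and a 10% allowance for withdrawal or exclusion (Section 8.2), monitoring from 20 to 36/37 weeks, and a crossover at about 8 weeks (Section 5.6).

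- Nominal: 50 × 16 = 800 woman-weeks, of which 50 × 8 = 400 are on the Doppler.
- After the allowance, 50 × 0.9 = 45 women. Counting nothing from those who leave, 45 × 16 = 720, of which 45 × 8 = 360 are on the Doppler.
- If monitoring runs to 37 weeks, it lasts 17 weeks and the second period 9. Doppler use is then 8/17 = 47% or 9/17 = 53%, depending on sequence.

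The share is about half of home monitoring. It is not half of follow-up, because data collection runs from enrollment to the 6-8 week postpartum visit (Section 5.8). Some events will therefore start when no study device is in use.

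**Step 2: where an event in a Doppler week would end up.** Only one device is held at a time. An assessor asked about HeraBEAT would most naturally answer unrelated. The event stays in the record, but nothing says whether the Doppler played a part.

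**Step 3: whether the planned analysis separates the devices.** Each randomized arm is a sequence containing both devices:

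| Arm | First period | Second period |
|---|---|---|
| A | HeraBEAT | Doppler |
| B | Doppler | HeraBEAT |

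Over the whole study, comparing arm A with arm B compares orders of use. Events must be split by device-period to compare devices.

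**Step 4: what a symmetric rating could show.** The event rates here are assumptions, since the document gives none.

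- With zero related events in a device-period, the one-sided 95% upper limit is 1 − 0.05^(1/n): 6.4% for n = 45 and 5.8% for n = 50.
- Exact McNemar power, two-sided 5%, treating a woman's two periods as independent:

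| Assumed rates | n = 45 | n = 50 |
|---|---|---|
| 2% vs 10% | 15% | 20% |
| 5% vs 20% | 46% | 52% |
| 2% vs 20% | 73% | 79% |

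Only very large differences would be likely to show up in a test.

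**The case against.** HeraBEAT is the investigational device (Section 3.3), which is a fair reason to ask causality of it. No objective in Section 5.1 and no analysis in Section 8.0 promises a comparison of device-related events, and Hypothesis 2b does not mention attributed event rates. All events are recorded with severity and seriousness whichever device is in use, and the assigned device follows from sequence and gestational age. False alarms leading to visits are captured for both devices under Section 5.9.3, and urgent visits for fetal concerns are a secondary measure in Section 5.1. Section 5.7 is also a short summary of a form that is not in the document.

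Most of this stands, and it rules out three stronger readings that a reader might infer:

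- **Doppler events will be charged to HeraBEAT.** The document does not show this. Because the first device is returned at crossover, a lost Doppler link is likelier. Wrong attribution to HeraBEAT is plausible mainly around the crossover.
- **Safety cannot be compared between devices at all.** Only judged relatedness is one-sided. Crude incidence by period can be rebuilt if onset dates are kept.
- **The Doppler's related-event count is zero by construction.** Relatedness to the Doppler is simply never requested in the text, and the form may go further than the text.

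The objection does not close the gap. The other sources make no causality rating. A record of visits prompted by home readings cannot capture false reassurance, where a reading leads a woman not to seek care. The text does not commit to recording device at onset or to a table by device. Inferring the device from gestational age is weakest near a crossover that the plan itself places only approximately: "After approximately 8 weeks of monitoring, patients will complete a System Usability Survey (SUS Survey").

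**Conclusion.** The point holds in a limited form. Section 5.7 rates relatedness for one of two study-issued devices, leaving about half of home-monitoring exposure (nominally 400 of 800 woman-weeks, about 360 of 720 after withdrawals) without a causality question about the device in use. Judged device-related events cannot be compared like for like, and the default comparison between arms does not separate the devices.

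This is a reporting gap of modest severity. It rests on reading Section 5.7 as a full statement of the assessment; if the case report form already asks about both devices, only the text needs to change. The exposure figures assume that women follow the planned schedule.

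**What to change.** In Section 5.7 and on the case report form:

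- Record the onset date and the study device in use at onset: HeraBEAT, Doppler or none.
- Rate relationship to that study device, using the same categories for both.

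In Section 8.0, add a descriptive table of adverse events by device-period with woman-weeks of exposure, in place of a comparison by randomized sequence, and state that no formal test is intended. Include a row for events with no device in use, since collection continues to 6-8 weeks postpartum.

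The cost is about two form fields and one extra table, with no added burden on participants. If the form already holds these items, Section 5.7 need only say so. Adding them before enrollment avoids having to reconstruct device and relatedness afterwards.
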